8.3.1.1. Interruption of the Intravenous Infusion

The infusion should be interrupted if any of the following AEs are observed:

- Sustained/severe cough
- Rigors/chills
- Rash, pruritus (itching)
- Urticaria (hives, welts, wheals)
- Diaphoresis (sweating)
- Hypotension
- Dyspnea (shortness of breath)
- Vomiting
- Flushing

The reaction(s) should be treated symptomatically, and the infusion may be restarted at 50% of the original rate once symptoms resolve.

If investigators feel there is a medical need for treatment or discontinuation of the infusion other than described above, they should use clinical judgment to provide the appropriate response according to typical clinical practice.

For patients who experience infusion-related hypersensitivity reactions that are \leq grade 2 during infusion, infusion should be interrupted or infusion rate reduced. For those who plan to continue treatment, premedication listed below are recommended for re-treatment.

For grade 1 symptoms (mild reaction; infusion interruption not indicated; intervention not indicated), the following prophylactic medications are recommended for future infusions: diphenhydramine 50 mg (or equivalent) and/or acetaminophen/paracetamol 325 mg to 1000 mg at least 30 minutes prior to subsequent study treatment infusions.

For grade 2 symptoms (moderate reaction that requires therapy or infusion interruption, but for which symptoms resolve promptly with appropriate treatment such as antihistamines, nonsteroidal anti-inflammatory drugs, narcotics, corticosteroids, and/or IV fluids; prophylactic medications

indicated at ≤ 24 hours), the following prophylactic medications are recommended for future infusions: diphenhydramine 50 mg (or equivalent) and/or acetaminophen/paracetamol 325 mg to 1000 mg at least 30 minutes prior to subsequent study treatment infusions. If necessary, corticosteroids (up to 25 mg of hydrocortisone or equivalent) may be used.

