10.1.3. Other Events that Require Accelerated Reporting to Sponsor

The following events also require reporting to the sponsor (or designee) within 24 hours of learning of the event:

Symptomatic Overdose of Study Drug: Accidental or intentional overdose of at least 2 times the intended dose of study drug within the intended therapeutic window, if associated with an AE.

Pregnancy: Although pregnancy is not considered an AE, it is the responsibility of the investigator to report to the sponsor (or designee), within 24 hours of identification, any pregnancy occurring in a female during the study or within 6 months of the last dose of study drug. Any complication of pregnancy affecting a female study patient and/or fetus and/or newborn that meets the SAE criteria must be reported as an SAE. Outcome for all pregnancies should be reported to the sponsor.

Adverse Events of Special Interest (applicable to cemiplimab only): All AESI, serious and nonserious, must be reported within 24 hours of identification using the same reporting process as for SAE reporting, per Section 10.1.2. Adverse events of special interest for this study include the following:

The following will be considered AESI for this study:

- Grade ≥ 2 infusion related reactions
- Grade ≥ 2 allergic/hypersensitivity reactions
- Grade ≥ 3 imAEs (see Section 10.1.3.1)
- An imAE of any grade in a patient previously treated with a PI 3-K inhibitor

NOTE (Applicable to cemiplimab only): An imAE can occur shortly after the first dose or several months after the last dose of treatment. All AEs of unknown etiology associated with drug exposure should be evaluated to determine possible immune etiology. If an imAE is suspected, efforts should be made to rule out neoplastic, infectious, metabolic, toxin or other etiologic causes prior to labeling an AE as an imAE.

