10.2.5. Severity

The severity of AEs, infusion reactions, and injection site reactions will be graded using the NCI-CTCAE v5.0 grading system. Adverse events not listed in the NCI-CTCAE v5.0, will be graded according to the following scale:

- 1 (Mild): Mild AE (minor; no specific medical intervention; asymptomatic laboratory findings only, radiographic findings only; marginal clinical relevance)
- 2 (Moderate): Moderate AE (minimal intervention; local intervention; noninvasive intervention [packing, cautery])
- 3 (Severe): Severe and undesirable AE (significant symptoms requiring hospitalization or invasive intervention; transfusion; elective interventional radiological procedure; therapeutic endoscopy or operation)
- 4 (Life-threatening): Life-threatening or disabling AE (complicated by acute, life threatening metabolic or cardiovascular complications such as circulatory failure, hemorrhage, sepsis. Life-threatening physiologic consequences; need for intensive care or emergent invasive procedure; emergent interventional radiological procedure, therapeutic endoscopy or operation)
- 5 (Death): Death associated with an AE.

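### Protocol Section 8.3.1.1 gives conflicting instructions for a mild infusion reaction, so sites may handle it differently and grade it differently around the grade 2 AESI threshold

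*Protocol*

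**What the plan says.** Four statements in Protocol Section 8.3.1.1 bear on a mild reaction during a cemiplimab infusion.

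- The symptom list opens with "The infusion should be interrupted if any of the following AEs are observed". Cough must be sustained or severe to count. The other entries, among them flushing, pruritus and sweating, carry no severity threshold.
- Directly after the list: "The reaction(s) should be treated symptomatically, and the infusion may be restarted at 50% of the original rate once symptoms resolve".
- For infusion-related hypersensitivity reactions of grade 2 or lower, "infusion should be interrupted or infusion rate reduced".
- The advice on premedication for later infusions then describes the two grades. Grade 1 reads "For grade 1 symptoms (mild reaction; infusion interruption not indicated; intervention not indicated". Grade 2 reads "For grade 2 symptoms (moderate reaction that requires therapy or infusion interruption".

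Elsewhere, Section 10.2.5 names the scale: "The severity of AEs, infusion reactions, and injection site reactions will be graded using the NCI-CTCAE v5.0 grading system". Sections 8.3.1 and 10.2.4 both point to it. Section 10.1.3 lists "Grade ≥ 2 infusion related reactions" among the AESIs to be reported within 24 hours, and SAP Section 4.5.2 repeats that threshold. AESI incidence and severity belong to a secondary endpoint (Protocol 4.2). SAP Section 5.8.1 tabulates both IRRs and AESIs by grade.

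**The concern.** A site whose patient flushes mildly during the infusion has no single instruction to follow. One sentence requires a stop, another accepts a slower rate, and the grade 1 wording says that neither stopping nor intervening is called for.

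The conflict can reach the data because the section describes severity partly through the action taken. A site that obeys the list has interrupted the infusion and treated the patient. If it then turns to the only IRR-specific grade descriptors printed in the protocol, it may conclude that the event was not grade 1. The boundary between grades 1 and 2 is also the AESI threshold for IRR, so the choice decides whether the event goes into expedited reporting and into the AESI table. With one arm, no internal comparison would show whether the IRR AESI rate reflects severity or the way sites read the section.

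**Working it through.** The plan states no figure on this point and no arithmetic applies. The check is to follow one case, mild flushing during the infusion, through the text.

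1. **Symptom list (8.3.1.1).** Flushing is listed without a severity qualifier. Result: interrupt.
2. **Sentence after the list (8.3.1.1).** Result: treat the symptoms, with an optional restart at half the original rate.
3. **Sentence for grade 2 or lower (8.3.1.1).** Grade 1 is included. Result: interrupt or slow the rate. This already differs from step 1, which offers no slower rate as an alternative.
4. **Grade 1 descriptor (8.3.1.1).** Result: neither interruption nor intervention is indicated. This conflicts with steps 1 and 2, and with both options in step 3.
5. **Grade 2 descriptor (8.3.1.1).** A moderate reaction that needs therapy or interruption. After steps 1 and 2 the patient has had both, but the reaction was mild. The action half of the descriptor fits and the severity half does not.
6. **Recorded grade (10.2.5).** NCI-CTCAE v5.0 governs. Neither document says how an interruption made only because the list requires it should affect that grade.
7. **AESI threshold (Protocol 10.1.3, SAP 4.5.2).** Grade 2 counts and grade 1 does not, so an unsettled grade leaves AESI status unsettled.

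Next, does any rule elsewhere resolve the conflict?

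- Section 8.2.4 says that more detailed sections, including 8.3, override its own general guidance. It does not rank sentences within 8.3.
- The clinical-judgment sentence in 8.3.1.1 covers needs beyond those already described. It does not choose between the instructions given.

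Finally, how far does it reach?

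- Fever, back pain, abdominal pain and nausea are typical IRR symptoms in Section 8.3.1 but are not on the interruption list. For them the conflict is between steps 3 and 4 only.
- Section 8.3.1 allows onset up to 24 hours after the infusion ends, when there is nothing left to interrupt.
- Neither document gives an IRR incidence or a grade distribution.

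**The case against.** The strongest reply is that the conflict never reaches the recorded grade. Sections 8.3.1, 10.2.4 and 10.2.5 all assign grading to NCI-CTCAE v5.0, and the parentheses in 8.3.1.1 merely introduce premedication advice. Grade 2 there means a moderate reaction, so a mild one that was interrupted does not fit. The sentence for grade 2 or lower itself contemplates a grade 1 reaction that was interrupted or slowed.

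This reply defeats one stronger reading. A reader might infer that following the list turns mild reactions into grade 2 AESIs. No sentence in either document says so, and the three points above count against it. What remains is that some sites may grade that way.

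A reader might also try to size the effect. Suppose any-grade IRR occurs in 5% to 15% of 105 patients and half of these are clinically grade 1: 105 × 0.05 × 0.5 = 2.6 and 105 × 0.15 × 0.5 = 7.9. Both rates are assumptions with no source in the documents. The result is also a ceiling, because it takes every such reaction to involve a listed symptom, to start during the infusion and to be upgraded. The supported lower bound is zero.

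The reply is also right that the practical effect is limited. The case report form captures symptoms, interruption, rate reduction and medication (8.3.1), so grading can be checked. All IRRs are tabulated by grade apart from AESIs, so grade 1 events stay visible. Safety analysis is descriptive and no decision rule uses the AESI rate. Permanent discontinuation for IRR starts at grade 3. The recommended antihistamine and paracetamol premedication is the same for grades 1 and 2, with optional corticosteroid added at grade 2.

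None of this removes the contradiction in the instruction to the site.

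**Conclusion.** The point stands as an internal contradiction in Section 8.3.1.1 that no other section resolves. For a mild reaction with a listed symptom, the list, the sentence for grade 2 or lower and the grade 1 descriptor call for different actions. Handling may differ between sites. Grading may differ too, so some mild reactions may be recorded as grade 2 and hence as AESIs. That last step assumes that some sites grade from the wording in 8.3.1.1 or from the action taken, instead of applying Section 10.2.5 on its own. The documents neither require nor exclude this.

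The number of patients affected cannot be derived from the documents. What could shift is the split of IRRs between grades 1 and 2 and the IRR part of the AESI summary, which is a secondary safety endpoint. The primary analysis of objective response rate is unaffected. Which clinical instruction is right is not judged here.

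**What to change.** Reconcile the symptom list, the sentence on treating symptoms, the sentence for grade 2 or lower and the grade 1 and grade 2 descriptors in Section 8.3.1.1, so that one consistent instruction applies to each grade. The sponsor chooses the clinical rule. Align the descriptors with the scale named in Section 10.2.5, and say in 8.3.1.1 that the recorded grade comes from that section.

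A trial-specific rule on whether an interruption raises or leaves the grade is not needed. It would modify an external scale whose treatment of interruption the documents do not show.

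The cost is protocol wording at the next amendment and a note to sites. No new data are needed. No SAP change is needed either, since the SAP analyses the grades that are recorded.

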8.3.1.2. Termination of the Intravenous Infusion

The infusion should be terminated and NOT restarted if any of the following AEs occur:

- Anaphylaxis*
- Laryngeal/pharyngeal edema
- Severe bronchospasm
- Chest pain
- Seizure
- Severe hypotension
- Other neurological symptoms (confusion, loss of consciousness, paresthesia, paralysis, etc.)
- Any other symptom or sign that, in the opinion of the investigator, warrants termination of the IV infusion

*Consider anaphylaxis if the following is observed ([Sampson, 2006](#)): acute onset of an illness (minutes to several hours) with involvement of the skin, mucosal tissue, or both (eg, generalized hives, pruritus or flushing, swollen lips-tongue-uvula) AND AT LEAST ONE OF THE FOLLOWING

- Respiratory compromise (eg, dyspnea, wheeze-bronchospasm, stridor, reduced peak expiratory flow, hypoxemia)
- Reduced BP or associated symptoms of end-organ dysfunction (eg, hypotonia [collapse], syncope, incontinence)

8.3.1.3. Local Injection Site Reactions

Local ISRs must be reported as AEs and graded according to Section [10.2.5](#).

8.3.1.3.1. Management of ISA101b-Specific Adverse Events

ISA101b will be discontinued for any severe (\geq grade 3) ISR. Severity will be graded according to Section [10.2.5](#).

ISA101b administration should be delayed for the following:

- Any \geq grade 3 ISA101b-related AE.
- Temperature $>38^{\circ}\text{C}$ over the last 24 hours prior to administration.
- Any AE, laboratory abnormality, or intercurrent illness which, in the judgment of the investigator, warrants delaying the dose of ISA101b.

The occurrence of an ISA101b -associated systemic allergic reaction will be managed according to standard practice, including close observation, antihistamines, and fluids, as well as steroids or epinephrine if clinically indicated. ISA101b should not be administered again following resolution of a grade 4 systemic allergic reaction. Refer to the ISA101b Investigator's Brochure for details.

Local ISR at site(s) of previous administration of ISA101b of > grade 3 should be treated symptomatically and followed until resolution to grade 1 is observed.

Patients may resume treatment with the next dose of ISA101b when study drug-related AEs resolve to grade ≤ 1 or baseline value, with the following exception: patients may resume treatment in the presence of grade 2 fatigue.

If day 29 of ISA101b is missed, the second dose of ISA101b will be given on day 45 (± 3 days) and the third dose will be given on day 66 (± 3 days). If day 29 was missed due to an AE or lab abnormality, this must have resolved prior to resumption of dosing.

If day 50 of ISA101b is missed, the third dose of ISA101b will be given on day 66 (± 3 days). If day 50 was missed due to an AE or lab abnormality, this must have resolved prior to resumption of dosing.

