1.3.3. Safety Profile

Clinical experience in approximately 100 patients who have received ISA101 indicates that the most common AEs associated with ISA101 are local ISRs. The ISRs were dose related and observed in approximately 90% of the patients who received the RP2D of 100 µg/peptide. In addition, systemic allergic reactions have been observed, particularly in patients receiving higher doses of 300 µg/peptide (33%) compared to <5% at the 100 µg/peptide dose.

Based on its composition and initial clinical data, ISA101b appears to have a comparable safety profile to ISA101. The available safety data with ISA101b indicate that it has an acceptable safety profile for use at 100 µg/peptide. The most frequent toxicities are local ISRs (predominantly grade 1 to 2). Systemic allergic reactions are potentially the most serious adverse reactions to ISA101/ISA101b.

No overlapping toxicities of ISA101/ISA101b with either chemotherapy (paclitaxel and carboplatin) or anti-PD-1 therapy (nivolumab) have been detected. No autoimmune AEs have been reported in relationship to HPV-16-SLP, ISA101 or ISA101b. Immune-mediated treatment-emergent adverse events (TEAEs) have been reported with anti-PD-1 antibodies. For further information on ISA101b regarding appropriate recommendations and precautions, refer to the ISA101b Investigator's Brochure.

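### Protocol 8.3.1.3.1 gives two instructions for a grade 3 injection site reaction, stop ISA101b or delay and resume it, and does not say which governs

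*Protocol*

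**What the plan says.** All the conflicting text is in Protocol 8.3.1.3.1.

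- **Stop.** "ISA101b will be discontinued for any severe" ISR, with severe defined there as grade 3 or higher. The sentence does not say whether the stop is permanent.
- **Delay.** "ISA101b administration should be delayed for the following" opens a list whose first entry is any "grade 3 ISA101b-related AE", carrying an at-or-above sign. ISRs are not excepted.
- **Resume.** "Patients may resume treatment with the next dose of ISA101b when study drug-related AEs resolve to grade" 1 or lower, or baseline. The only exception named is grade 2 fatigue.
- **Catch-up.** If day 29 is missed, doses 2 and 3 move to days 45 and 66; if day 50 is missed, dose 3 moves to day 66 (each ±3 days). A dose missed because of an adverse event is expressly covered.

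Elsewhere the Protocol makes clear that an ISR is an ISA101b-related adverse event: "Local ISRs must be reported as AEs and graded according to Section" 10.2.5 (8.3.1.3), and "the most common AEs associated with ISA101 are local ISRs" (1.3.3).

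**The concern.** A patient with a grade 3 ISR satisfies the condition of the stop sentence and the condition of the delay entry. One site could end vaccination. Another could wait for grade 1 and give the next dose. Both could point to the same section.

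The main stake is patient protection: whether a patient is re-dosed after a severe reaction would depend on which sentence the site applies. The second stake is interpretation of the vaccine component. Protocol 1.3.2 reports that the HPV16-specific response was substantially increased after two or three doses of ISA101, and the hypothesis in 3.1 ties response to vaccine-induced T cells, so the number of doses is relevant. The third is reporting. SAP 5.6.2 summarizes the number of doses and dose intensity, and SAP 5.8.1 tabulates adverse events leading to *permanent* treatment discontinuation. Whether a grade 3 ISR enters that table could reflect the site's reading and not the event.

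**Working it through.** **1. Does a grade 3 ISR meet both conditions?** Yes. It is an ISR of grade 3 or higher (stop sentence) and an ISA101b-related adverse event of grade 3 or higher (delay entry).

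**2. Does any other text rank the two?**

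| Protocol section | What it does | Settles a grade 3 ISR? |
|---|---|---|
| 8.2.2.1, permanent stops | Covers any grade 4 non-hematologic toxicity, apart from clinically insignificant laboratory findings; does not name ISRs | No; largely settles grade 4 |
| 8.2.2.2, temporary stops | Points to 8.3, among others, for interruption criteria | No |
| 8.2.4, precedence clause | Puts 8.2.4 below the more detailed sections, including 8.3 | No; it does not order sentences inside 8.3.1.3.1 |

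**3. Doses under each reading.** The plan is three doses, on days 1, 29 and 50 (Protocol 6.1).

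| Grade 3 ISR after | Stop reading | Delay-and-resume reading | Largest difference |
|---|---|---|---|
| Dose 1 | 1 dose (day 1) | up to 3: days 1, 45, 66 if day 29 is missed | 2 of 3 doses (67%) |
| Dose 2 | 2 doses (days 1, 29) | up to 3: days 1, 29, 66 if day 50 is missed | 1 of 3 doses (33%) |
| Dose 3 | 3 doses | 3 doses | none |

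Under the second reading, *up to* is needed because the event must come down in time for the next dose. If it does so before the planned day, the original days 1, 29 and 50 stand.

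**4. How this appears in the SAP exposure summary.** SAP 5.6.2 takes exposure in weeks as (last dose − first dose + 21)/7, assuming here that neither data cut-off nor death comes sooner. Relative dose intensity is (total dose/exposure) ÷ (planned dose/3). With k doses of equal size, this reduces to 3k/exposure.

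- Day 1 only: exposure 21/7 = 3.0 weeks; 3 × 1/3.0 = 1.00.
- Days 1, 29: (28 + 21)/7 = 7.0 weeks; 3 × 2/7.0 = 0.86.
- Days 1, 45, 66, or days 1, 29, 66: (65 + 21)/7 = 12.29 weeks; 3 × 3/12.29 = 0.73.
- Days 1, 29, 50 as planned: (49 + 21)/7 = 10.0 weeks; 3 × 3/10.0 = 0.90.

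A patient stopped after one dose therefore shows a higher relative dose intensity than one who receives all three. The difference between the readings would be visible in the count of doses, not in this ratio.

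**5. Number of patients.** The documents give no rate of ISRs at grade 3 or higher. As an assumption: 1% × 105 = 1.05 and 5% × 105 = 5.25, so about 1 to 5 patients. At 10% it would be 10.5.

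**6. Primary endpoint.** The full analysis set is every enrolled patient who received any study drug (Protocol 11.3.1, SAP 3.1). Both readings keep the same patients in the denominator, so the precision in Protocol Table 3 is unchanged.

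**The case against.** The best reply is that the specific rule governs the general one. The ISR sentence comes first and is mandatory, the delay list is general, and the resume sentence is permissive. Protocol 8.2.1 treats delay, interruption and discontinuation of ISA101b as separate actions, so once the vaccine is discontinued there is no dose left to delay. The section uses the same structure for a grade 4 systemic allergic reaction: it falls within the delay entry, yet its own sentence bars further dosing.

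This is a plausible reading, and many sites may adopt it. But the text does not state it, and the comparison with the allergic reaction cuts both ways: that sentence expressly rules out another dose, and the ISR sentence does not. Elsewhere (8.2.2.1, 8.2.3.2, 8.3.1) the Protocol writes *permanent* or *permanently* when it means that, while 8.2.2.2 uses *discontinuation* for temporary stops and names 8.3 as a source of criteria. The ambiguity survives, though as a drafting overlap and not a plain reversal.

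A reader might also infer more than the documents support:

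- **That most patients are exposed to the conflict.** The 85% to 90% ISR frequency in Protocol 1.3.2 is any-grade, and 1.3.3 describes ISRs as predominantly grade 1 to 2. In the 24-patient ISA101 plus nivolumab study, the six ISRs named are listed under grade 1 to 2.
- **That there is a second conflict over resumption.** For a missed day 29 the text says "If day 29 was missed due to an AE or lab abnormality, this must have resolved prior to resumption of dosing", with a matching sentence for day 50. The natural meaning of resolved is the threshold in the paragraph just before.
- **That an exactly grade 3 ISR is left without follow-up.** The sentence reads "Local ISR at site(s) of previous administration of ISA101b of > grade 3 should be treated symptomatically and followed until resolution to grade 1". A lost bar under the inequality sign when the PDF was read would produce this wording, so no finding should rest on it until the source is checked.

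**Conclusion.** The point holds for grade 3 ISRs: one section gives two instructions and does not say which prevails or whether the stop is permanent. The difference is at most two of three doses after dose 1, at most one of three after dose 2, and none after dose 3. The count of about 1 to 5 patients in 105 rests wholly on an assumed 1% to 5% rate, and the dose differences assume the event comes down in time for the next dose.

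The inference that the response-rate estimate is compromised is not supported: its denominator and planned precision are the same under either reading. What remains open is consistent protection of patients after a severe reaction, together with the ISA101b exposure and discontinuation summaries. Few patients are involved, but the rule concerns re-dosing and is cheap to make clear.

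**What to change.** Reconcile the discontinue, delay and resume sentences of Protocol 8.3.1.3.1 so that a single stated rule governs an ISR of grade 3 or higher, and state whether *discontinued* there means permanently. Which rule applies is for the sponsor to decide; this review takes no position on it. While editing, check the sign before grade 3 in the treat-and-follow sentence against the source document.

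The cost is a few sentences in the next amendment or a clarification letter to sites. No extra visits, data or analyses are needed.
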